## **2 STUDY OBJECTIVES**

### **2.1 Objectives**

The objectives of this study are the following:

- To evaluate the safety and tolerability of multiple doses of CIN-102 in subjects with idiopathic or diabetic gastroparesis
- To evaluate the effect of multiple doses of CIN-102 on gastric emptying as measured by the gastric emptying breath test (GEBT) in subjects with idiopathic or diabetic gastroparesis
- To characterize the PK of multiple doses of CIN-102 in subjects with idiopathic or diabetic gastroparesis

### **2.2 Exploratory Objectives**

The exploratory objectives of this study include the following:

- To assess the effect of multiple doses of CIN-102 on nausea associated with gastroparesis based on the nausea score on the American Neurogastroenterology and Motility Society Gastroparesis Cardinal Symptom Index Daily Diary (ANMS GCSI-DD)
- To assess the effect of multiple doses of CIN-102 on ANMS GCSI-DD scores (total and subscales) in subjects with idiopathic or diabetic gastroparesis
- To assess the effect of multiple doses of CIN-102 on a variety of patient reported outcomes
- To characterize exposure-response relationships of CIN-102

### 3 STUDY DESCRIPTION

#### 3.1 Summary of Study Design

This is a randomized, double-blind, placebo-controlled Phase 2A study to evaluate safety, efficacy, PK, and dose response of oral CIN-102 in adults with idiopathic or diabetic gastroparesis.

The study will begin by randomizing subjects in Cohort 1 to either CIN-102 [REDACTED] BID or placebo BID in a ratio such that 15 subjects receive CIN-102 and 5 subjects receive placebo. Subjects will opt into either a sparse pharmacokinetic sampling subgroup or an intensive PK sampling subgroup. The study will be stratified at randomization by idiopathic versus diabetic gastroparesis. Efforts will be made to ensure adequate numbers of idiopathic and diabetic gastroparetic subjects are included. After approximately 15 subjects in Cohort 1 complete the study, an independent Data Review Committee (DRC) will convene to review the data from Cohort 1. The Data Review Committee will review emerging safety, PK, and/or efficacy data throughout the study to determine if it is safe and appropriate to continue the study with the currently planned dose levels for Cohorts 2 and 3 or if further refinement of the proposed dose levels is warranted. Currently planned dose levels for Cohorts 2 and 3 are [REDACTED] BID and [REDACTED] BID, respectively, with 15 subjects receiving the study drug and 5 subjects receiving placebo in each cohort. However, these planned dose levels may be modified and/or additional cohorts may be added based on emerging information from the current study as well as other ongoing studies. The highest dose will not exceed [REDACTED] BID and no more than 40 additional subjects will be added without a protocol amendment. The DRC will also determine how to advance the cohorts (serially or simultaneously). Further details regarding the role, responsibilities, and procedures of the DRC will be provided in the DRC Charter.

At the Screening Visit, all subjects will sign informed consent prior to any study procedures being performed. Subjects must meet all of the inclusion criteria and none of the exclusion criteria to be eligible for study participation.

Subjects will be evaluated as follows:

- Days -28 to -11: Screening procedures will be performed. [REDACTED]  
[REDACTED]
- Day -10 to -3: [REDACTED] A GEBT will be performed on a single day within this window with breath samples obtained twice prior to consumption of a standardized, C-enriched meal and then at 45, 90, 120, 150, 180, and 240 minutes after meal consumption after an 8-hour fast. [REDACTED]  
[REDACTED]  
[REDACTED]
- Day -3 to -1: A Pre-Randomization visit will be completed to perform safety assessments and to allow adequate turnaround time of lab results prior to Day 1 (Randomization).
- Days 1 to 14: Study drug will be administered (CIN-102 or placebo BID for 14 (±2 days) and safety assessments will be performed; [REDACTED]  
and PK blood sampling will be completed at specified timepoints. [REDACTED]  
[REDACTED]  
[REDACTED].

Note: Day 14 ( $\pm 2$  days): A GEBT will be administered 30 minutes after study drug administration on Day 14 ( $\pm 2$  days). Breath samples will be obtained twice prior to  $^{13}\text{C}$  enriched meal consumption and then at 45, 90, 120, 150, 180, and 240 minutes after meal consumption after an 8-hour fast. If a subject withdraws from the study prior to the Day 14 ( $\pm 2$  days) GEBT, attempts should be made to perform a GEBT on the last day of study drug administration. [REDACTED]

Subjects will be stratified at randomization based on their etiology for gastroparesis (ie, diabetic gastroparesis versus idiopathic gastroparesis).

[figure not shown]
On days of the GEBT, subjects will present at the clinic after an overnight fast and should take regular medications, including any treatment for diabetes, with the exception of any prohibited concomitant medication. Subjects will self-administer their usual morning insulin injection, taking into consideration their fasting status. Subjects will be instructed to bring in their study medication and additional insulin, as needed, to the clinic. Fasting blood glucose will be assessed before study drug administration and gastric emptying assessments to ensure a blood glucose of  $\leq 275$  mg/dL. Additional insulin may be given (prorated based on meal caloric content) to ensure a blood glucose of  $\leq 275$  mg/dL prior to the gastric emptying procedure. Likewise, Investigators should manage low blood sugar (hypoglycemia;  $< 60$  mg/dL) as per their discretion.

Safety will be evaluated through assessments of adverse events, vital signs, physical examinations, clinical laboratory evaluations (including prolactin), and ECG findings. Additionally, a single, optional pharmacogenomic (PGx) blood sample may be collected at any time during the subject's participation in the study.

Subjects will have follow-up visit(s) 1 to 3 days after the final dose of study drug to assess adverse events, changes to concomitant medications (including use of rescue medications), vital signs, and for PK sampling. Subjects participating in the intensive PK subgroup will be seen in the clinic on Day 15 and Day 16 (+1 day). Subjects participating in the sparse PK subgroup will have the option to complete either the Day 15 Visit or the Day 16 (+1 day) Visit. Unscheduled visits and/or additional follow-up may be required at the discretion of the Investigator. For example, subjects with clinically significant abnormal laboratory findings, unresolved treatment-emergent adverse events (TEAEs), serious adverse events (SAEs) that require follow-up laboratories and review, or clinically significant adverse events may necessitate further assessments.

Figure 1 presents a study schematic.

**Figure 1. Study Schematic**

\* Anticipated dose level

\*\* For each cohort, patients will be randomized to CIN-102 or placebo. Randomization will occur on the morning of Day 1.

\*\*\*Patients participating in the intensive PK subgroup will be seen in the clinic on Day 15 and Day 16 (+1 day). Patients participating in the sparse PK subgroup will be seen on Day 15 OR Day 16 (+1 day).

BID = 2 times daily; DRC = Data Review Committee; GEFT = gastric emptying breath test.

### **3.2 Study Indication**

CIN-102 is being developed for the treatment and relief of symptoms associated with acute and recurrent gastroparesis.

### **3.3 Dose Escalation and Review Committee**

A DRC consisting of at least three members, including a cardiologist, a clinical pharmacologist, and an independent clinician experienced in the treatment of patients with idiopathic or diabetic gastroparesis will be formed to review emerging PK and safety data in a blinded manner.

The DRC will convene to review safety and efficacy data through at least Day 14 from approximately 15 of the subjects in each cohort. PK data from approximately 8 subjects receiving CIN-102 in each cohort will be considered adequate for DRC review (these PK data may be a combination of the sparse PK scheme and the intense PK from a subset of subjects). In the event a subject discontinues the study at least 24 hours after steady-state is believed to have been achieved (based on available data from the SAD and MAD studies) for a reason unrelated to safety, the existing data from that individual may be sufficient for decision making by the DRC.

Dose escalation will only take place after the DRC has determined that is appropriate (eg, adequate safety and tolerability have been demonstrated and PK behavior is well enough characterized to support proceeding to a higher dose level and/or study of a lower dose level or frequency is meaningful based on emerging safety data).

Upon each DRC review, the following may occur:

- proceed to the next protocol-specified dose level or
- proceed to alternate dosing regimen(s) not to exceed the next protocol-specified dose level

Further detail on DRC conduct will be described in the DRC Charter.

#### **3.3.1 Criteria for Temporary Suspension of Dosing**

Dosing within a cohort or between cohorts will be temporarily suspended until a full cumulative data review is complete if any of the following occur:

- Any study drug-related SAE grade 3 or higher based on Common Terminology Criteria for Adverse Events (CTCAE) Version 5.0
- Any single subject whose ECG (average triplicate ECGs as interpreted by central read) demonstrates a heart-rate corrected QTcF interval (QTcF) >500 msec or in whom there is an increase in QTcF >60 msec from baseline (confirmed by repeat ECG)
- Any new ECG abnormality deemed clinically significant by the investigator
- Any study drug-related cardiac adverse event. In the event that a subject experiences a vasovagal or near-syncopal episode, dosing within a cohort or subsequent cohort may proceed as planned unless the episode is associated with ECG abnormality or the event is deemed to be severe in intensity (severity) by the Investigator
- A study drug-related adverse event from a single System Organ Class deemed to be of moderate intensity (severity) in 4 or more subjects

- Any of the following laboratory abnormalities that are thought to be study drug-related or in which an alternative explanation is not reasonable:
  - ALT or AST  $>8 \times$  the upper limit of normal (ULN), or
  - ALT or AST  $>5 \times$  ULN and persist for more than 2 weeks, or
  - ALT or AST  $>3 \times$  ULN in conjunction with elevated total bilirubin  $>2 \times$  ULN or international normalized ratio  $>1.5$ , or
  - ALT or AST  $>3 \times$  ULN with appearance of fatigue, nausea, vomiting, right upper quadrant pain or tenderness, fever, rash, and/or eosinophilia ( $>5\%$ )
- Any single subject who develops serious study drug-related electrolyte abnormalities due to vomiting and/or inability to maintain adequate oral hydration that impacts cardiac stability
- Other conditions as deemed medically appropriate based on the Investigator's judgement

The Sponsor and/or DRC may also suspend dosing for any other reason based on emerging data. Should dosing be temporarily suspended, the DRC can review and discuss all available safety and PK data from all subjects participating in the study up until the time of the event. The DRC will decide whether knowledge of the treatment assignment of any subject(s) is(are) necessary to make an appropriate decision about continuation of the study. If so, a request to unblind will be made and relevant data will be reviewed in an unblinded manner. All unblinding Standard Operating Procedures will be followed and documented as appropriate.

Upon completion of the cumulative data review (whether fully blinded or partially unblinded), the DRC may elect to terminate the study or to resume study conduct. If study conduct is resumed, the DRC may elect to do one of the following:

- Continue dosing in the current cohort with the same number of subjects originally planned
- Expand the current cohort with additional subjects to obtain more information at that dose level
- Escalate to a higher dose level
- Increase the frequency of dosing at the current dose level (if the protocol-specified number of subjects at the current dose level have already completed)
- De-escalate to a lower dose level
- Decrease the frequency of dosing at the current dose level

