### 3.3.2 Criteria to Cease Dose Escalation

Dosing within a cohort or between cohorts will cease if either of the following occurs:

- Any two grade 3 or 1 grade 4 or higher study drug-related SAE based on CTCAE Version 5.0
- Any 2 subjects with an ECG (average of triplicate ECGs as determined by central read) demonstrating QTcF  $>500$  msec or a change in QTcF  $>60$  msec from baseline (confirmed by repeat ECG with central read)

Should one of the above occur, consideration may still be given to continued study of an alternate dose level or frequency (either expansion of a previously studied cohort or addition of a lower dose level).

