### 8.1.3 Assessment of Adverse Events by the Investigator

The Investigator will assess the severity (intensity) of all adverse events (serious and non-serious) and will be graded using the CTCAE Version 5.0 criteria as shown in Table 1. The Investigator will also categorize each adverse event as to its potential relationship to study drug using the categories of yes or no.

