## 8.2 Serious Adverse Events

An adverse event or adverse reaction is considered serious if, in the view of either the Investigator or Sponsor, it results in any of the following outcomes:

- Death.
- A life-threatening adverse event.

Note: An adverse event or adverse reaction is considered “life-threatening” if, in view of either the Investigator or Sponsor, its occurrence places the subject at immediate risk of death. It does not include an event that, had it occurred in a more severe form, might have caused death.

- Requires hospitalization or prolongation of existing hospitalizations.

Note: Any hospital admission with at least 1 overnight stay will be considered an inpatient hospitalization. An emergency room or urgent care visit without hospital admission will not be recorded as a SAE under this criterion, nor will hospitalization for a procedure scheduled

or planned before signing of informed consent, or elective treatment of a pre-existing condition that did not worsen from Baseline. However, unexpected complications and/or prolongation of hospitalization that occur during elective surgery should be recorded as adverse events and assessed for seriousness. Admission to the hospital for social or situational reasons (ie, no place to stay, live too far away to come for hospital visits, respite care) will not be considered inpatient hospitalizations.

- A persistent or significant disability/incapacity or substantial disruption of the ability to conduct normal life functions.
- A congenital anomaly/birth defect.
- An important medical event.

Note: Important medical events that do not meet any of the above criteria may be considered an SAE when, based upon appropriate medical judgment, they may jeopardize the subject and may require medical or surgical intervention to prevent 1 of the outcomes listed above. Examples of such medical events include allergic bronchospasm requiring intensive treatment in an emergency room or at home, blood dyscrasias or convulsions that do not result in inpatient hospitalizations, or the development of drug dependency.

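### The organ-class suspension rule counts only moderate drug-related events, so a severe but non-serious event can leave untriggered a pause that a milder event would have made mandatory

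*Protocol*

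**What the plan says.** Protocol section 3.3.1 lists the events that suspend dosing, within or between cohorts, until a full cumulative review is done. Two items concern adverse events in general:

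- "Any study drug-related SAE grade 3 or higher based on Common Terminology Criteria for Adverse Events (CTCAE) Version 5.0"
- "A study drug-related adverse event from a single System Organ Class deemed to be of moderate intensity (severity) in 4 or more subjects"

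The other specific items cover QTcF and other ECG findings, drug-related cardiac events, liver tests, and serious electrolyte disturbance that affects cardiac stability. The list ends with an item left to the investigator's judgement. A following paragraph adds: "The Sponsor and/or DRC may also suspend dosing for any other reason based on emerging data". SAP section 2.2.3.1 repeats the list, with the organ-class item unchanged.

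The stricter rule in Protocol section 3.3.2 also works through serious events: "Any two grade 3 or 1 grade 4 or higher study drug-related SAE based on CTCAE Version 5.0". Its other limb is QTcF only.

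Protocol section 8.1.3 has the investigator grade every adverse event, serious or not, on CTCAE Version 5.0. Table 1 makes grade 2 moderate and grade 3 severe. Section 8.2 defines seriousness by outcome, not by grade.

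**The concern.** A rule that counts toxicity should not become harder to meet as the toxicity gets worse. This one names a single grade and sets no floor. If one of four subjects with grade 2 events in an organ class has a grade 3 event instead, and that event is not serious, the count drops from four to three and the mandatory pause is lost.

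The organ-class count is the only mandatory numeric rule for non-serious toxicity outside the cardiac, ECG, liver and electrolyte items. Protocol section 1.4 lists depression, anxiety, somnolence, akathisia and rash among the effects reported with domperidone, so organ classes that depend on this rule are relevant to this drug. At stake is whether dosing is held for review when events are worse than those that already make a hold compulsory. No efficacy estimate is affected.

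**Working it through.** The documents state no error rate or operating characteristic for this rule, so there is no figure of the plan's own to reproduce. The check is one of logic, followed by an illustration on assumed rates.

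**Step 1. Does any mandatory rule count a related, non-serious, grade 3 event in, say, the skin or nervous system class?**

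| Rule | Counts it? | Reason |
|---|---|---|
| Grade 3 or higher (3.3.1) | No | Requires an SAE |
| Organ-class count (3.3.1) | No | Moderate only; Table 1 makes grade 3 severe |
| QTcF, ECG, cardiac, liver and electrolyte items (3.3.1) | No | Different events |
| Cease-escalation rule (3.3.2) | No | Requires an SAE, or QTcF |
| Investigator, Sponsor or DRC (3.3.1) | Only if invoked | Judgement, no threshold |

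An event can be grade 3 without being serious. Table 1 allows grade 3 for loss of self-care without admission, and section 8.2 says that an emergency visit without admission does not meet the hospitalization criterion.

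**Step 2. Apply the rule to cases** (one organ class, all events related, grade 3 events non-serious, one event per subject).

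| Subjects with grade 2 | Subjects with grade 3 | As written | With *moderate or greater* |
|---|---|---|---|
| 4 | 0 | Suspend | Suspend |
| 3 | 1 | No | Suspend |
| 2 | 2 | No | Suspend |
| 0 | 4 | No | Suspend |
| 0 | 15 | No | Suspend |

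**Step 3. Size of the effect on this rule alone.** Inputs: n = 15 subjects on CIN-102 in a cohort (Protocol section 3.1) and the threshold of 4 (section 3.3.1). Assumed: r, the rate of moderate or severe non-serious related events in one class, and s, the share of those that are severe.

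As written, P(fires) = P(X ≥ 4) with X ~ Binomial(15, p) and p = r(1 − s). Corrected, p = r.

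Example with r = 0.20 and s = 0.25: p = 0.20 × 0.75 = 0.15. P(0), P(1), P(2) and P(3) are 0.0874, 0.2312, 0.2856 and 0.2184, which sum to 0.8227 before rounding. P(fires) = 1 − 0.8227 = 0.1773.

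| r | s = 0% | s = 25% | s = 50% | s = 100% | Corrected, any s |
|---|---|---|---|---|---|
| 10% | 5.6% | 2.2% | 0.5% | 0% | 5.6% |
| 20% | 35.2% | 17.7% | 5.6% | 0% | 35.2% |
| 30% | 70.3% | 44.6% | 17.7% | 0% | 70.3% |

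**Step 4. Add the SAE rule.** Now let r cover serious events too, and let f be the share of severe events that are serious. One such event pauses dosing by itself. With q = rsf:

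P(pause) = 1 − (1 − q)^15 × P(Y ≤ 3), with Y ~ Binomial(15, p′).

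As written, p′ = r(1 − s)/(1 − q). Corrected, p′ = r(1 − sf)/(1 − q).

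At r = 0.20 and s = 0.25:

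| f | q | (1 − q)^15 | p′ as written | P(pause) as written | p′ corrected | P(pause) corrected |
|---|---|---|---|---|---|---|
| 0 | 0 | 1 | 0.150 | 17.7% | 0.200 | 35.2% |
| 50% | 0.025 | 0.684 | 0.154 | 44.6% | 0.179 | 50.5% |
| 80% | 0.040 | 0.542 | 0.156 | 56.5% | 0.167 | 58.3% |

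The wording costs 17.4, 6.0 and 1.9 percentage points (differences of the unrounded values).

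**The case against.** **The word may be meant as a minimum.** The vasovagal clause in the same list sets its threshold at severe with no *or higher*, and a life-threatening episode cannot be meant to escape it. So the list does not mark floors consistently, and the authors may have intended at least moderate here. That is plausible, but neither document says it, the first item in the list does state a floor, and a site that applies Table 1 literally would not count a grade 3 event.

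**Most grade 3 events may be serious.** Each part of the grade 3 definition has a near counterpart in section 8.2: admission, disability, disruption of normal life, and important medical events, which qualify where "they may jeopardize the subject and may require medical or surgical intervention to prevent 1 of the outcomes listed above". One related grade 3 SAE pauses dosing. This stands and shrinks the gap, as Step 4 shows. If half of the severe events or more are serious, the full set of rules in that example pauses more often than the 35.2% seen with no severe events at all. The gap remains for grade 3 events that meet none of those outcomes.

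**The count of 15 is itself an assumption.** Section 3.3.1 limits the count neither to one cohort nor to CIN-102 subjects. Because relatedness is judged blind, placebo events can count. A subject with a grade 3 event and a separate grade 2 event in the same class would also still count. Both points make the illustration approximate; neither changes Step 2.

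**Discretion covers the rest.** The investigator's item and the Sponsor or DRC can stop dosing, individual subjects can be withdrawn under section 4.4, and "Dose escalation will only take place after the DRC has determined that is appropriate". These are real protections. But the scheduled DRC review uses Day 14 data from about 15 subjects per cohort, whereas the suspension rule also acts during a cohort. And the plan removes discretion for four moderate events, so it is inconsistent to rely on discretion for worse ones.

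**Conclusion.** The concern holds. As written, three grade 2 events plus one non-serious grade 3 event in an organ class do not trigger the pause that four grade 2 events do. This follows from the text and needs no assumed rate.

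The practical size is modest and uncertain. It depends on how often severe related events are non-serious, which the documents do not say. The Step 3 table describes this one rule, not the whole safety scheme. With the SAE rule included, the loss in the worked example ranges from 17.4 percentage points when no severe event is serious to 1.9 points when 80% are. In practice the gap concerns grade 3, since a grade 4 event would normally be serious as life-threatening. It should be corrected because it is a stated, mandatory safety threshold that gives the wrong result.

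**What to change.** In Protocol section 3.3.1 and SAP section 2.2.3.1, change the intensity in the organ-class item to *moderate or greater*, keeping the threshold of four subjects. No other item needs to change.

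The cost is two words in each document. Grade and relatedness are already recorded, and events are already coded to organ class. Dosing may be paused for review somewhat more often, but only when severe non-serious events occur. For this rule alone, with n = 15, an assumed total rate of 10% and one event in ten severe (p = 0.09), the chance of a pause rises from 4.0% to 5.6%. At 20% with a quarter severe it rises from 17.7% to 35.2%. With no severe events nothing changes, and any pause lasts only until the cumulative review is complete.
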